## Rationale and Specific Aims

The primary objective of this study is to determine whether a patient with a tibial plateau fracture (non-displaced, displaced, depression type) will have decreased pain and narcotic analgesia requirements following an intra-articular injection of local anesthetic and aspiration of the knee. In order to determine whether this institution has an appropriate volume of tibial plateau fractures to adequately perform such a trial, we have reviewed our volume of tibial plateau fractures and have determined we have an adequate volume to conduct such a study. The primary outcome of the study could potentially guide future management of tibial plateau fractures at this institution and potentially systemically.

- a) Specific Aim 1: Examine the effect of hemarthrosis aspiration and intra-articular bupivacaine injection on recorded Numerical Rating Scale (NRS) pain scores for patients with tibial plateau fractures in the first 24 hours following injury.**
- Working Hypothesis: Hemarthrosis aspiration and intra-articular bupivacaine injection will significantly decrease subjective pain scores in the early post-injury period.*

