  - As stated previously, there has been substantial research to support the aspiration of fracture hematoma with intra-capsular injuries as it has been shown to decrease pain in the immediate presentation. There has been no research regarding intra-articular injection of local anesthetics in the acute setting of tibial plateau fractures, though there are several studies showing the efficacy of intra-articular anesthetics following total knee arthroplasty and various knee arthroscopic procedures involving the knee. There exist several methods for collecting subjective pain scores. One of the most common pain assessment tools, and the tool documented most in our institution is the VAS. To truly collect VAS data, one must use a 10cm or 100mm rule and have the patient point or state the area on the ruler than most appropriately depicts their current level of pain. The left most position represented by zero is “no pain” whereas the right most position, represented by 10cm or 100mm, is “maximal pain.” However, this method is infrequently carried out in clinical practice and as such we have chosen to use a validated Numerical Rating Scale (NRS) for pain. NRSs range from 0 to 10 and were validated for emergency department patients. One validation study demonstrated that the verbally administered NRS (0 representing “no pain” and 10 representing “maximal, excruciating pain”) had a strong correlation with the VAS. This suggests that for patients who are asked to quantify their pain on a scale of 0-10 after tibial plateau fractures, the NRS is equivalent to using VAS pain scales but with easier reproducibility among varying clinical team members.

**b) Preliminary studies 1.1: Analgesic Effect of Intraarticular Bupivacaine or Morphine After Arthroscopic Knee Surgery: A Randomized, Prospective, Double-Blind Study.**

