For the patients randomized into the treatment arms, the knee will be held in 15-30\* short of full extension and fully prepped using chlorhexidine wipes in a centrifugal manner. An 18 gauge spinal needle will be introduced into the superolateral aspect of the knee (if the knee is too edematous, an inferolateral or inferomedial approach is appropriate, but requires documentation). Aspirate the knee with 60cc syringe until unable to draw out more fluid and record volume on

given study form. Remove the syringe from the needle connection, leaving the 18 gauge needle in place. Draw up 30cc of 0.5% bupivacaine with 1:200,000 epinephrine (Marcaine) with .18-gauge needle into 2nd 60cc syringe. Place the filled syringe on the 18 gauge needle already in the knee and INJECT. Remove needle-syringe construct and place bandage over injection site.

The patient's initial NRS score will be recorded immediately. Subsequent VAS scores will be recorded at time points 0 (5 minutes after intervention), 2, 4, 6, 8, 12, 24 hours after initial work-up of the patient. Patients treated as an outpatient will record these values themselves (copy of recording form submitted with this application). Patients will be directed to bring the completed form with them to their regular clinic follow-up visit. Additionally, supplemental analgesia requirements will be recorded upon administration and will be converted to morphine equivalent units for analysis (copy of recording form submitted with this application). All patients admitted to the orthopedic service will be placed on morphine PCA (determined dosing by weight of patient). All other patients (those admitted to other services) will have analgesia converted to Opioid Morphine Equivalents (OMEs).

Prospectively: Patients will be blinded to initial management of the tibial plateau fracture with either: Aspiration of the knee joint alone, aspiration of the joint and injection of bupivacaine 0.5% with epinephrine or no injection or aspiration therapy for a control arm. Using the block randomization list, the patient will be randomization at the time of consent for participation. The patient's initial VAS score will be recorded at the time of initial work-up. Subsequent VAS scores will be recorded at time points 2, 4, 6, 8, 12, 24 hours after initial work-up of the patient. Additionally, supplemental analgesia requirements will be recorded upon administration and will be converted to morphine equivalent units for analysis.

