### **Statistical Considerations**

Sample sizes of 22, 22, and 22 will be allocated to 3 groups (control, aspiration, and aspiration plus injection) using an equal 1:1:1 block randomized allocation. The null hypothesis is that at 24 hours the mean VAS score for these three groups will be equivalent. Power is computed to reject this null hypothesis. A total sample of 66 subjects achieves 84% power to detect at least one pairwise minimal difference score of 1.60mm using the Tukey-Kramer (Pairwise) multiple comparison test at a 0.05 significance level. An assumption was made to set the common standard deviation of the VAS score within any one group to 1.00mm.

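### The stated 84% power does not follow from the plan's own inputs, which give about 99.8% or more; those inputs are also in VAS millimetres although a 0-10 NRS was chosen

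*Combined protocol and SAP*

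**What the plan says.** The only sample-size justification is in Statistical Considerations. It allocates 22 patients to each of control, aspiration, and aspiration plus injection. The null hypothesis is equal mean VAS at 24 hours in the three groups, and the section adds: "Power is computed to reject this null hypothesis". The result is given as "A total sample of 66 subjects achieves 84% power to detect at least one pairwise minimal difference score of 1.60mm", by the Tukey-Kramer pairwise test at 0.05. For variability, an assumption was made to "set the common standard deviation of the VAS score within any one group to 1.00mm". The section gives no source for the 1.60 or the 1.00, no pattern for the three means and no dropout allowance.

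On the scale, Specific Aim 1 in Rationale and Specific Aims refers to "recorded Numerical Rating Scale (NRS) pain scores for patients with tibial plateau fractures". The text under that aim says that for a true VAS "one must use a 10cm or 100mm rule", that this is seldom done in practice, and "as such we have chosen to use a validated Numerical Rating Scale (NRS) for pain. NRSs range from 0 to 10". Study Procedures uses both names. One paragraph reads "initial NRS score will be recorded immediately. Subsequent VAS scores will be recorded at time points 0", and a later one says the "initial VAS score will be recorded at the time of initial work-up".

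**The concern.** A difference of 1.60 with an SD of 1.00 is a standardised difference of 1.6, which is very large for 22 patients per arm. One would expect power close to 100% even after adjustment for three comparisons, so 84% looked wrong on sight.

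The sentence is the whole case for enrolling 66 patients, 44 of whom (22 + 22) are assigned to a needle procedure. If its numbers disagree, a reader cannot tell whether 66 is more than double what is needed, about right, or too few. The unit label adds a second doubt about what size of pain difference the trial is meant to detect.

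**Working it through.** **Inputs, all from Statistical Considerations.** n = 22 per arm, k = 3 arms, largest difference d = 1.60, common SD σ = 1.00, Tukey-Kramer at family-wise α = 0.05. Error degrees of freedom are 3 × (22 − 1) = 63.

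**Critical value.** The studentized range q(0.95; 3, 63) is 3.395. On the t scale this is 3.395/√2 = 2.400.

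**Trying to reproduce the 84%**

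1. *Single pair.* Noncentrality = (d/σ) × √(n/2) = 1.60 × √11 = 5.307. The probability that a noncentral t with 63 df exceeds 2.400 in absolute value is 0.9978.
2. *At least one pair, the definition in the text.* This depends on where the middle mean lies, so it was simulated. Under equal means the simulated family-wise error was 0.0496, close to the nominal 0.05. Means 0, 0.8, 1.6 (the least favourable pattern with range 1.60) give 0.998. Means 0, 0, 1.6 give 0.9998.
3. *Omnibus F, reading the stated null hypothesis literally.* Noncentrality = n × Σ(μᵢ − μ̄)²/σ². For 0, 0.8, 1.6 it is 22 × (0.64 + 0 + 0.64) = 28.16, giving power 0.9980. For 0, 0, 1.6 it is 22 × 1.707 = 37.5, giving 0.9999.
4. *Other variants.* A Bonferroni normal approximation gives 99.8%, unadjusted tests 99.96%, and Tukey at α = 0.01 for a single pair 98.7%. Loss to 18 per arm gives 99.1% (any pair, evenly spaced means). Swapping the two inputs (difference 1.00, SD 1.60) gives 42% to 53%.

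None of these is 84%.

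**What would give about 84%**

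| Quantity changed, others as stated | Any pair, means 0, d/2, d | Any pair, means 0, 0, d | Single pair |
|---|---|---|---|
| Difference, at SD 1.00 and 22 per arm | about 1.01 | about 0.88 | about 1.03 |
| SD, at difference 1.60 and 22 per arm | about 1.59 | about 1.81 | about 1.56 |
| Smallest n per arm reaching 84%, at 1.60 and 1.00 | 10 (86.8%) | 8 (86.7%) | 10 (85.6%) |

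On the stated inputs, then, 24 to 30 patients in total (3 × 8 to 3 × 10) would already reach 84%.

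**If the SD is larger.** The document gives no observed SD, so every value here is an assumption. Difference 1.60:

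| Assumed SD | Single pair, 22 per arm | Any pair, evenly spaced, 22 per arm | n per arm for about 84% any-pair power, evenly spaced (total) |
|---|---|---|---|
| 1.5 | 87% | 88% | 20 (60) |
| 2.0 | 60% | 63% | 35 (105) |
| 2.5 | 40% | 44% | 54 (162) |

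**Units.** Power depends on d/σ, here 1.60/1.00, and both terms carry the same label, so the label cannot account for the 84%. It does affect meaning. Read literally on a 100 mm rule, 1.60 mm is 1.60/10 = 0.16 of a point on a 0-10 scale. If the label is a slip for centimetres or points, the target is 1.60 points, ten times larger.

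**The case against.** The best defence is that the error is conservative. On the stated inputs power is understated, so nothing shows that 66 is too few. If the power is the misprint, 66 is more than enough. If the difference is the misprint and should be about one SD, 66 still gives about 84%. Harm follows only if the SD is wrong, and the document does not show that it is. All of this stands. It limits the claim to a sentence that cannot be right as written, and it makes the larger-SD table illustrative only.

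A second defence is that 84% might be all-pairs power under means that were not reported. All-pairs power does vary widely: 29.6% for means 0, 0.8, 1.6, 82% for 0, 1.6, 2.6 and 99.6% for 0, 1.6, 3.2. But the text defines power by at least one pair. A pattern that comes near 84%, such as 0, 1.6, 2.6, has a smallest gap of about 1.0, not 1.60. With 1.60 as the smallest gap the means span at least 3.2, and all-pairs power for 0, 1.6, 3.2 is 99.6%.

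Unstated dropout does not help either: about 9 to 10 evaluable patients per arm would have to remain (82% and 87%, evenly spaced means).

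On the scale, the protocol treats the NRS as interchangeable with the VAS, so much of the mixed naming is loose terminology. That is fair, and the point is secondary. The millimetre label still leaves the target effect unclear by a factor of ten.

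**Conclusion.** The concern holds. The stated 84% should be about 99.8% (99.8% to 99.98% across patterns of means with range 1.60), given 22 per arm, a difference of 1.60, an SD of 1.00 and Tukey-Kramer at 0.05. The type II error is about 0.2%, against the 16% implied. The calculation assumes normal scores with equal variance and no losses; allowing for loss to 18 per arm does not change the conclusion.

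At least one of the difference, the SD and the power is wrong as written, and the document does not identify which. It is not shown that the trial is underpowered. If the SD is at fault and the difference of 1.60 stands, power for at least one pair drops below 84% once the SD exceeds about 1.6 (evenly spaced means) to 1.8 (two arms equal). The VAS-millimetre label is a separate inconsistency with the chosen 0-10 NRS.

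**What to change.** Rewrite the power paragraph in Statistical Considerations so that the difference, SD, power and assumed pattern of the three means agree. If 1.60 and 1.00 are what the team intended, report about 99.8%. Otherwise correct the wrong input and report the power that 66 patients give. State where the SD comes from, and confirm the sample size only once it is justified.

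Express the difference and SD in 0-10 NRS points, and use one scale name in Study Procedures and Statistical Considerations that matches Specific Aim 1. A short power table over plausible SDs, and power for any single contrast the team wishes to name, would be useful but optional.

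The cost is one rewritten paragraph and a few changes of scale name. No extra patients follow from the correction itself. If the sourced SD proves to be above about 1.6 to 1.8 at a difference of 1.60, the team must either accept power below 84% or revisit the sample size.

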## **Enrollment/Randomization**

Sample sizes of 22, 22, and 22 will be allocated to 3 groups (control, aspiration, and aspiration plus injection) using an equal 1:1:1 block randomized allocation.

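### Single-step Tukey-Kramer is valid but stricter than three arms require: after one pair is rejected, the other two can be tested at unadjusted 0.05 with family error still at 5%

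*Combined protocol and SAP*

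**What the plan says.** - **Arms and size** (Enrollment/Randomization, repeated in Statistical Considerations): "Sample sizes of 22, 22, and 22 will be allocated to 3 groups (control, aspiration, and aspiration plus injection"). Patients are randomised in blocks, in equal numbers per arm.
- **Null** (Statistical Considerations): "The null hypothesis is that at 24 hours the mean VAS score for these three groups will be equivalent".
- **Power and test** (Statistical Considerations): the plan claims 84% power with 66 patients in total and a 0.05 level. The target is "at least one pairwise minimal difference score of 1.60mm using the Tukey-Kramer (Pairwise) multiple comparison test".
- **Variability** (Statistical Considerations): "An assumption was made to set the common standard deviation of the VAS score within any one group to 1.00mm".
- **Aim 1 hypothesis** (Rationale and Specific Aims): "Hemarthrosis aspiration and intra-articular bupivacaine injection will significantly decrease subjective pain scores in the early post-injury period". Aim 2 makes the parallel claim for supplemental opioid use. Neither aim names a comparator.

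Tukey-Kramer appears only in the power statement, but it is the only comparison method that the document names. No primary contrast and no testing order are given.

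**The concern.** Single-step Tukey applies one critical value to every pair, whatever the other pairs show. With four or more arms that strictness does some work after a first rejection. With three arms it does not. If one pair of means differs, the two remaining equalities cannot both be true, so at most one true null is left to reject wrongly. Holding the remaining pairs to the Tukey value then adds nothing to control of the family error.

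The comparisons most exposed are the smaller ones. A trial with control, aspiration, and aspiration plus injection can show what each component adds, and each component step may be smaller than the full effect of the combination. Those are the pairs for which a threshold of 2.40 rather than 2.00 can decide the result.

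**Working it through.** **Inputs from the plan.** Three arms of 22, so error df = 66 − 3 = 63; difference 1.60; SD 1.00; alpha 0.05. Only the ratio of difference to SD matters, so the mm label does not affect the results.

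**Critical values.** Tukey: q(0.95; 3, 63)/√2 = 3.394/1.414 = 2.400. Unadjusted two-sided 0.05: t(0.975; 63) = 1.998.

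**The plan's own figure.** The noncentrality for one pair is λ = difference / (SD × √(2/22)), with √(2/22) = 0.3015. For 1.60 and SD 1.00, λ = 1.60/0.3015 = 5.31. The noncentral t probability of exceeding 2.400 on 63 df is 99.8%. For at least one pair, simulation gives 99.8% to 100% over the mean patterns tried. The stated 84% is not reproduced. Per-pair power of 84% needs an SD of about 1.56: λ = 1.60/(1.56 × 0.3015) = 3.40. That SD is used below as an assumption; it is not a figure in the plan.

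**The step-down rule.** Order the three |t| values. The largest must exceed 2.400. If it does, test each of the other two against 1.998. This is a closed test: any two of the three pairwise equalities together imply that all three means are equal, so the only joint hypothesis is the overall null. The Tukey range test covers that at 5%, and each single pair is then tested at 5%. Any pair that Tukey rejects exceeds 2.400, so the largest does too; no Tukey rejection is lost.

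**Family error by simulation.** 5.0% with all means equal; 5.0% with two arms equal and the third far away.

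**Power, 22 per arm.** The placement of the aspiration arm is an assumption throughout, as is every SD other than 1.00.

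| Setting | Pair | λ | Tukey | Step-down |
|---|---|---|---|---|
| SD 1.00, aspiration = control | full 1.60 | 5.31 | 99.8% | 99.9% |
| SD 1.00, aspiration halfway | each 0.80 step | 2.65 | 60% | 74% |
| SD 1.56, aspiration halfway | each 0.80 step | 1.70 | 25% | 38% |
| SD 1.56, aspiration = control | combined vs aspiration, 1.60 | 3.40 | 84% | 89% |
| SD 2.0, aspiration = control | combined vs aspiration, 1.60 | 2.65 | 60% | 67% |

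**Fixed sequence, for comparison.** Test combined versus control first at 0.05, then combined versus aspiration. With a 1.0 SD difference and aspiration halfway (assumptions), power for combined versus control is 82% with Tukey, 83% with step-down and 90% with the fixed sequence. For combined versus aspiration, with a 1.60 difference and aspiration equal to control, the fixed sequence gives 61% against Tukey's 60% at SD 2.0, and 39% against 40% at SD 2.5.

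**The case against.** The strongest defence is that nothing is wrong. Tukey-Kramer suits a null of three equal means, and it supplies simultaneous intervals that agree with its tests. At the plan's difference and SD, a sharper test gains about 0.1 point. All of this stands. It makes the point one of efficiency, and it means that gains may be quoted only with their assumptions attached.

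Two stronger readings are tempting, and the documents support neither.

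- *Any significant pair would count as success for Aim 1.* The words about at least one pair define the power calculation. They are not a success rule, and Tukey-Kramer gives a separate result for each pair, so aspiration versus control would be reported as that.
- *The aims ask about a single contrast, so aspiration versus control is idle.* The aims name the combined treatment without a comparator, and the stated null covers all three groups. The Background and the Rationale and Specific Aims also give a separate case for aspiration itself. Combined versus control is a natural reading, but it is an inference.

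**Conclusion.** The point holds as an improvement to a valid method. With three arms, single-step Tukey is needlessly strict after the first rejection, and the step-down test is at least as powerful for every pair at the same 5% family error.

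The size of the gain depends on quantities that the plan does not give. It is negligible for a pair that differs by the full 1.60 at SD 1.00. It is 13 to 14 points for a half-size step (60% to 74% at SD 1.00; 25% to 38% at SD 1.56). It is 5 to 7 points for combined versus aspiration at 1.60 when aspiration equals control and the SD is 1.56 to 2.0. A reader might expect the same gain on combined versus control; the step-down does not give it (82% to 83% at 1.0 SD, aspiration halfway). The rise to 90% belongs only to a fixed sequence that tests that contrast first.

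The failure of the stated 84% to follow from its own inputs is a separate defect in the same paragraph, and it should be settled first because it bears on which SD is credible.

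**What to change.** 1. In Statistical Considerations, reconcile the difference, SD, number per arm and stated power, and state whether the power is per pair or for at least one pair.
2. State the analysis, for example: *The three pairwise differences at 24 hours will be compared using the pooled variance. The largest will be tested against the Tukey critical value at familywise 0.05. Only if it is significant will the remaining two pairs each be tested at unadjusted two-sided 0.05.*
3. If Tukey intervals are still reported, say that they are simultaneous intervals and that the step-down test may reject a pair whose Tukey interval includes zero.

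The cost is a change of wording, with no added patients or assessments, and the loss of an exact match between tests and simultaneous intervals.

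Optional, for the sponsor to weigh: name aspiration plus injection versus control as the first test at 0.05, with the other pairs tested only if it succeeds. This raises power on that contrast. It gives up any stand-alone finding for aspiration when the first test fails, and it does not reliably help combined versus aspiration at larger SDs. If this order is chosen, the aims should name the comparator.

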- This study randomized patients undergoing arthroscopy of the knee into 3 arms: injection of normal saline (n=49), 0.25% bupivacaine (n=44), or 0.03% morphine (N=46) at the end of the procedure and VAS scores were recorded at times 3, 6, 12, and 24 hours post-operatively. The VAS data were analyzed using analysis of covariance (ANCOVA). VAS was analyzed only for treatment effect in this study. Bupivacaine provided significant postoperative analgesia compared to morphine or saline (where no statistically significant difference was demonstrated). Figure 1 demonstrates the VAS scores for the 3 arms of the study showing that the effect of Intra-articular bupivacaine was noted for all 24 hours of data collection. Additionally, the study found that the time to first supplemental

**Figure 1.** Visual analogue scale (VAS) scores for the three groups who received general anesthesia. The time  $\times$  treatment effect was not statistically significant ( $F = 0.31, P = 0.96$ ) but the treatment effect was significant ( $F = 5.49, P = 0.006$ ). Post-hoc analysis using the Newman-Keuls test showed the bupivacaine group ( $n = 28$ ) to have significantly lower VAS scores than either of the other two groups ( $P < 0.05$ ). There was no difference between the morphine ( $n = 36$ ) and placebo ( $n = 27$ ) groups ( $P = 0.32$ ).

analgesia was increased in both the morphine and bupivacaine arms compared to the placebo.

**c) Specific Aim 2: Determine if patients who undergo hemarthrosis aspiration and intra-articular bupivacaine injection use less supplemental opioid analgesia.**

a. *Working Hypothesis: Intra-articular aspiration and bupivacaine injection will significantly decrease the patients' use of supplemental opioid analgesia in the early post-injury period.*

**Preliminary Studies 2.1: Intra-Articular Injection of Bupivacaine in Knee-Replacement Operations: Results of Use for Analgesia and for Preemptive Blockade.**

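### The stated 84% power does not follow from a 1.60 difference with an unsourced SD of 1.00; 22 per arm gives 84% near 1.0 SD, and less at the effect derivable from the plan's own preliminary study

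*Combined protocol and SAP*

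**What the plan says.** Statistical Considerations takes the 24-hour score as the endpoint for sizing: "The null hypothesis is that at 24 hours the mean VAS score for these three groups will be equivalent". It then claims: "A total sample of 66 subjects achieves 84% power to detect at least one pairwise minimal difference score of 1.60mm". The procedure named for this claim is Tukey-Kramer, with a familywise level of 0.05. The variability enters in one sentence: "An assumption was made to set the common standard deviation of the VAS score within any one group to 1.00mm". No pilot figure, citation or range supports that SD.

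The study headed Preliminary studies 1.1, under Rationale and Specific Aims, is offered in support of Aim 1. It compared intra-articular bupivacaine, morphine and saline after knee arthroscopy. Its figure legend gives a treatment effect of F = 5.49, P = 0.006, on 28 bupivacaine, 36 morphine and 27 placebo patients, with P = 0.32 between morphine and placebo. The plan prints no means or SDs from it.

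On institutional data, Rationale and Specific Aims says "we have reviewed our volume of tibial plateau fractures", and of pain scales that "the tool documented most in our institution is the VAS".

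**The concern.** A difference of 1.60 with an SD of 1.00 is an effect of 1.6 SD, which is large, and it rests on an SD that the plan itself calls an assumption. Two things then go wrong. The printed power is not the power those inputs give. And if someone repairs only the arithmetic, the paragraph will show a higher power while still resting on the unsupported SD.

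The stake is how the result is read. A null finding from a trial described as having 84% power invites the conclusion that the treatment does not help. That reading is sound only if the effect and SD behind the 84% are credible, and the plan's own cited evidence can be used to test whether they are.

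**Working it through.** **Inputs.** From Statistical Considerations: n = 22 per arm, three arms, difference 1.60, SD 1.00, Tukey-Kramer at 0.05. From Preliminary studies 1.1: F = 5.49, groups of 28, 36 and 27, and morphine-placebo P = 0.32. The units of the pain scale cancel in everything below, because power depends only on d = difference / SD.

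**Step 1: the plan's own figure.** Error df = 66 − 3 = 63. The studentized-range critical value is 3.395, so a pair is significant when |t| > 3.395 / √2 = 2.40. The noncentrality for one pair is d × √(22/2) = 1.6 × 3.317 = 5.31. The noncentral t distribution gives power of 99.8%; a normal approximation, Φ(5.31 − 2.40) = Φ(2.91), agrees. Any-pair power, from 200,000 simulated trials, is 99.8% with means 0, d/2, d and above 99.9% with means 0, 0, d. The overall F test gives 99.8% to 99.99%, and a Bonferroni-adjusted two-group formula gives 99.8%. All-pairs power is 99.6% with two means equal and 29% with evenly spaced means. No variant gives 84%.

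**Step 2: what 84% corresponds to.** With 22 per arm, 84% is reached at about d = 1.03 for one given pair, and at about 0.87 (two means equal) to 1.01 (evenly spaced) for any pair. An SD of 1.60 with the 1.60 difference would give 83.6% any-pair power with evenly spaced means, but the plan does not state that SD. At 1.6 SD, about 10 per arm would already give 86% for one pair.

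**Step 3: the effect implied by the preliminary study.** F on (2, 88) df at 5.49 has P = 0.0057, in line with the printed 0.006 and with one observation unit per patient (91 patients). Then Σn(m − m̄)²/σ² = 2 × 5.49 = 10.98.

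- If morphine equals placebo: d = √(10.98 / (28 × 63/91)) = √(10.98/19.38) = 0.75.
- A morphine-placebo P of 0.32 corresponds to t of about 1.00, hence a gap g of 1.00 × √(1/36 + 1/27) = 0.25 SD. Solving 28d² + 36g² − (28d + 36g)²/91 = 10.98 with g = +0.25 and −0.25 gives d = 0.86 and 0.57 for bupivacaine against placebo.
- The 95% limits for the noncentrality are 1.0 and 27.1. If morphine equals placebo, these give d = √(1.01/19.38) = 0.23 to √(27.1/19.38) = 1.18.

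The range 0.57 to 0.86 reflects only the unknown direction of the morphine-placebo gap. The sampling interval is the wider one, 0.23 to 1.18.

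**Step 4: power with 22 per arm.**

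| d (SD) | d × 3.317 | One given pair | Any pair, means 0, d/2, d | Any pair, means 0, 0, d |
|---|---|---|---|---|
| 0.57 | 1.89 | 31% | 36% | 46% |
| 0.75 | 2.49 | 54% | 58% | 70% |
| 0.86 | 2.85 | 67% | 70% | 82% |
| 1.00 | 3.32 | 82% | 84% | 92% |
| 1.60 | 5.31 | 99.8% | 99.8% | >99.9% |

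**Step 5: sensitivity to the SD for a 1.60 difference.** An SD of 2.0 (assumed) gives d = 1.60/2.0 = 0.80, with 60% for one pair and 64% to 76% for any pair. An SD of 2.5 (assumed) gives d = 0.64, with 40% for one pair and 44% to 55% for any pair.

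**The case against.** A reader might infer that the trial is sized for 1.6 SD while the plan expects 0.6 to 0.9 SD, so that the design assumes about twice the effect its evidence supports. The documents do not bear that out, for four reasons.

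- The sample is not what 1.6 SD requires. It delivers 84% near 1.0 SD, so the practical gap is about 1.0 against 0.57 to 0.86 SD.
- The plan never adopts the arthroscopy effect. The only effect it states is 1.60, described as a minimal difference, and a detectable difference need not equal an earlier study's estimate.
- The preliminary study is a different comparison: bupivacaine against saline after arthroscopy, with no aspiration described. The trial sets aspiration plus bupivacaine with epinephrine against no procedure in acute fractures, and the Background suggests that relieving joint pressure may itself reduce pain. The F averages 3 to 24 hours and comes from an analysis of covariance, so the derived SD units may not be those of a raw 24-hour score. The P-value match does not settle the model, since 86, 87 or 88 error df all give P = 0.0057.
- The interval of 0.23 to 1.18 SD includes 1.0 SD, where 84% does apply.

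All of this stands, and it limits the preliminary study to indirect evidence. None of it supplies a source for the SD of 1.00 or reconciles 84% with the stated inputs.

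Two further inferences should also be left out. Study Procedures says that fracture patterns differ in energy and may affect pain management, but gives this as a reason to classify them; it says nothing about the size of the SD. Nor can it be said flatly that a real benefit would more likely than not be missed: at 0.75 SD every power in the table exceeds 50%.

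**Conclusion.** The power statement needs correcting on two counts. First, its figures are mutually inconsistent: the stated inputs give above 99%, and 84% belongs to about 1.03 SD for one pair or about 0.9 to 1.0 SD for any pair. This follows from the plan's own numbers. Second, the SD is unsourced, so a corrected figure of over 99% would be no more trustworthy than the 84%.

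Across 0.57 to 0.86 SD, power is below 84% on every definition: 31% to 67% for one pair, 36% to 70% for any pair with evenly spaced means, and 46% to 82% with two means equal. These figures assume that the printed F is a patient-level test on 91 patients and that the arthroscopy effect carries over. The second assumption is weak, so they show how sensitive the power is and do not predict this trial's effect. The conclusion is not that the trial is too small, but that the plan does not show the power it claims.

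**What to change.** Keep 66 patients and rewrite the sample-size paragraph.

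1. Replace the 84% statement. Say that 22 per arm gives about 84% any-pair power near 1.0 SD with evenly spaced means, and state whether any-pair power or power for a named pair is meant.
2. Add a short power table over a range of SDs for the 1.60 difference (for a single pair, 60% at an assumed SD of 2.0 and 40% at 2.5) and at the preliminary-study effect (0.57, 0.75 and 0.86 SD), noting that this evidence is indirect.
3. Source the SD from pain scores charted at the institution, if usable ones exist. This is not assured: the review described in the plan was of fracture volume, and the plan says that true VAS measurement is uncommon in practice. If no usable 24-hour scores are found, label the SD as an assumption and let the table carry the uncertainty.

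The cost is a chart look-up and a rewritten paragraph, with no extra patients. The downside is a less favourable stated power.
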